PET	positron emission tomography
PI	Principal Investigator
PPV	positive predictive value
PSA	prostate specific antigen
PSADT	PSA doubling time
PSMA	prostate-specific membrane antigen
PT	preferred term
RP	radical prostatectomy
RT	Radiation Therapy
SAE	serious adverse event
SPECT	single photon emission computed tomography
SOC	Standard of Care
SUV	Standardized uptake value
US	United States/Ultrasound

1. BACKGROUND & RATIONALE

1.1. Background

Prostate cancer is the most common cancer among men in the United States (US) with an estimated annual incidence of 161,360 cases; it also represents the second most common cause of cancer-related death in men.¹ The vast majority of men dying of prostate cancer succumb to metastatic and/or recurrent disease.² Conventional imaging modalities such as computed tomography (CT), magnetic resonance imaging (MRI), [^{99m}Tc] methylene diphosphonate (MDP) bone scan, or ultrasound are not able to determine the location of recurrent and/or metastatic prostate cancer, particularly at low prostate specific antigen (PSA) levels.^{3,4,5,6} Thus, imaging agents and modalities that will detect and localize the tumor, as well as small metastatic lesions, with high sensitivity and specificity are essential to more accurately diagnose and stage the disease, detect recurrence and metastases, and potentially monitor therapeutic response.

A number of new, targeted positron emission tomography (PET) tracers have been introduced for imaging prostate cancer.^{7,8,9,10,11,12} A novel, high specific activity, highly selective, low-molecular weight prostate-specific membrane antigen (PSMA)-targeted PET radiotracer, ¹⁸F-DCFPyL, has been investigated as an imaging agent for prostate cancer. Progenics has licensed ¹⁸F-DCFPyL (PyL) from Johns Hopkins University (JHU) in 2015; and Progenics plans to complete the clinical development program of PyL for the detection of recurrent and/or metastatic prostate cancer.

Refer to the Investigator's Brochure (IB) for detailed information on ¹⁸F-DCFPyL Injection.

1.1.1. Pharmaceutical and Diagnostic Background

¹⁸F-DCFPyL (PyL) is a small molecule radiolabeled with the positron-emitting radionuclide ¹⁸F and binds to the extracellular domain of PSMA with high affinity. PSMA is a trans-membrane, 750-amino acid type II glycoprotein primarily expressed in normal human prostate epithelium at very low levels, if at all, but is upregulated in prostate cancer, including metastatic disease. PSMA is a unique exopeptidase with reactivity toward poly-gamma-glutamated folates that is capable of sequentially removing the poly-gamma-glutamyl termini.^{13,14} Since PSMA is expressed by virtually all prostate cancers, it is a very attractive target for developing agents for the diagnosis and staging of this disease.^{15,16,17} In addition to high expression in malignant prostatic tissue and being directly related to tumor aggressiveness,¹⁸ PSMA has also been detected in renal proximal tubules, in cells of the intestinal brush border membrane, in rare cells in the colonic crypts, in brain, salivary glands,^{19,20} and in the neovasculature of nonprostatic solid carcinomas (e.g., renal cell, breast, colon, pancreas, melanoma, and lung carcinoma).^{13,21}

Radiolabeled anti-PSMA monoclonal antibodies (mAbs) have been used to detect prostate cancer nodal metastasis and recurrence. Although the use of radiolabeled anti-PSMA mAbs have been met with logistical and clinical limitations as an imaging agent, phase 1 and 2 therapeutic trials utilizing PSMA as a therapeutic target have shown early promising results.^{22,23} Nonetheless, while monoclonal antibodies hold promise for tumor detection and therapy, there has been relatively limited clinical success outside of hematological cancers due to their low permeability in solid tumors and slow clearance from the circulating blood pool.

Smaller molecular weight compounds with higher permeability into solid tumors are likely to provide a distinct and definitive advantage in achieving higher percent uptake per gram of tumor tissue and a high percentage of specific binding. Small molecules are also expected to have improved blood clearance and tissue distribution in normal tissues compared with antibodies, thus enhancing the target-to-background ratio and thereby making lesion detection more conspicuous. In the past several years, a number of investigational PSMA-targeted small molecules have been synthesized and labeled with various radioisotopes to be tested for use as imaging agents for prostate cancer. A single photon emission computed tomography (SPECT) agent, ^{99m}Tc-MIP-1404,^{24, 25, 26} has just completed its phase 3 study enrollment for the detection of clinically significant prostate cancer in patients with low grade disease. PET imaging agents, such as ¹²⁴I-MIP-1095, ¹⁸F-DCFCBC, ¹⁸F-DCFPyL, ¹⁸F-FACBC and ⁶⁸Ga-HBED-CC, have also generated much interest for their potential use in detecting metastatic prostate cancer. Of these, ⁶⁸Ga-HBED-CC (⁶⁸Ga-PSMA) has been more broadly studied at academic centers and mostly under retrospective protocols.

¹⁸F-DCFPyL (“PyL”) has been the subject of extensive investigation since its synthesis and characterization by investigators at JHU in 2011.^{27,28} Over the past few years, various versions of PyL have been synthesized and used in academic investigator-sponsored studies and on a compassionate use basis in the US, Canada, and Europe. Collectively, published study results suggest that ¹⁸F-DCFPyL PET/CT provide high image quality and visualize small prostate lesions with excellent sensitivity.^{29,30,31,32,33} Furthermore, F-18 tracers offer important practical advantages, including higher production capacity than PET radiopharmaceuticals labeled with other radionuclides, such as Ga-68, which would facilitate rapid patient access. The detection rate of ¹⁸F-DCFPyL PET/CT compares favorably with that of ⁶⁸Ga-PSMA PET/CT in patients with biochemical recurrence (BCR).³⁴ The results of the Dietlein *et al* study also showed that ¹⁸F-DCFPyL PET/CT provided high image quality and visualized small prostate lesions with excellent sensitivity. Thus, ¹⁸F-DCFPyL PET/CT promises to be a useful diagnostic to localize prostate cancer, including in patients with suspected recurrence of prostate cancer where there is a high unmet medical need.

1.1.2. Nonclinical Studies

The nonclinical studies conducted with DCFPyL and ¹⁸F-DCFPyL included biochemical activity, biodistribution in xenograft mice, small animal PET imaging, and a single dose IV toxicology study in rats. All of these studies were submitted by JHU to FDA under IND 121,064. Data from an enzyme inhibition assay showed that DCFPyL binds competitively to PSMA expressing LNCaP cells with a Ki of 1.1 nM. Studies in PSMA positive tumor bearing nude mice demonstrated significant tumor uptake and retention, coupled with a rapid clearance from non-target organs to provide support for the further development of ¹⁸F-DCFPyL as a radiopharmaceutical for detection and localization prostate cancer in man. Results from a 14-day single dose rat toxicology studies with DCFPyL resulted in a no observed adverse effect level (NOAEL) of 0.5 mg/kg, the highest dose tested. The maximum human mass dose of DCFPyL is expected to be 4 µg; thus, this represents an estimated safety margin of >1200-fold the human equivalent dose.

1.1.3. Previous Human Experience

Several investigator-initiated clinical studies with ¹⁸F-DCFPyL Injection have been completed at JHU under IND 121,064. Data from two completed clinical studies show that PET imaging with ¹⁸F-DCFPyL Injection is feasible and safe. Study J1418 was a first-in-human, phase 1/2 study, conducted to evaluate the radiation dosimetry, biodistribution, metabolism, and safety of ¹⁸F-DCFPyL Injection with PET/CT imaging in men with metastatic prostate cancer. Once safety was established, the utility of ¹⁸FDCFPyL PET/CT imaging to detect local, nodal, and/or metastatic prostate cancer was assessed in men with advanced prostate cancer. Study J1545 was a phase 2 single-center, open-label study in men diagnosed with biochemical recurrence of prostate cancer. The study was conducted to evaluate the safety of ¹⁸F-DCFPyL Injection, to determine the location of putative sites of metastatic disease by ¹⁸F-DCFPyL PET/CT, to correlate findings on ¹⁸F-DCFPyL PET/CT with conventional imaging, and to assess treatment response by ¹⁸F-DCFPyL PET/CT following six months of standard of care (SOC) therapy.

Biodistribution following administration of ¹⁸F-DCFPyL Injection and an optimal imaging time point were determined, and the radiation dose used was within limits for diagnostic radiotracers for PET.^{28,31} Physiologic accumulation of ¹⁸F-DCFPyL was found to correspond to the distribution of PSMA expressing organs. Accumulation in primary tumor and metastatic lesions was very high, suggesting that ¹⁸F-DCFPyL Injection can be used to prospectively detect residual tumor as well as regional or distance metastases with high sensitivity and specificity.^{32,33} Sensitivity and specificity with ¹⁸F-DCFPyL PET/CT in patients with at least localized intermediate risk prostate cancer who have undergone radical prostatectomy (RP) with lymphadenectomy was comparable to published ⁶⁸Ga-PSMA imaging data.^{30,35}

1.1.4. Ongoing Progenics-Sponsored Clinical Trial(s)

An open-label, non-randomized, phase 2/3, multi-center study (PyL 2301) is being conducted in the US and Canada to evaluate the safety and diagnostic performance of ¹⁸F-DCFPyL PET/CT imaging in patients with at least high-risk localized or metastatic prostate cancer. The study is entitled, **PrO**spective Phase 2/3 Multi-Center Study of ¹⁸F-DCFPyL PET/CT Imaging in Patients with **PR**ostate Cancer: **Ex**amination of Diagnostic Accurac**Y** (OSP**REY**; NCT02981368). Eligible subjects with at least high-risk prostate cancer defined by NCCN v.3.2016 who are planned for radical prostatectomy with pelvic lymph node dissection (cohort A), and subjects with radiologic evidence of local recurrence or new or progressive metastatic disease (cohort B) are enrolled and administered 9 mCi (333 MBq) ¹⁸F-DCFPyL Injection followed by PET/CT imaging within 1-2 hours post-dosing. Diagnostic performance characteristics of ¹⁸F-DCFPyL PET/CT imaging will be evaluated using histopathology as the truth standard. Overall, ¹⁸F-DCFPyL imaging agent has been well-tolerated.

For study details and current safety findings please refer to the IB for ¹⁸F-DCFPyL Injection.

1.2. Rationale for the Study

One of the most challenging aspects of the clinical management of prostate cancer is the development of disease recurrence after prostatectomy, radiotherapy, or other local treatment modalities.^{36, 37, 38} Disease recurrence (rising PSA) after initial definitive therapy, defined as a confirmed PSA value of ≥ 0.2 ng/mL after prostatectomy or ≥ 2 ng/mL above nadir after

radiation therapy, is known as biochemical recurrence (BCR) of prostate cancer.^{39,40} BCR after initial therapy may develop in 20-30% of patients.^{36,37} Although PSA is the primary biomarker for recurrence, its values cannot determine the location or the extent of disease burden of recurrent and/or metastatic disease. PSA kinetics, such as PSA velocity as measured by PSA doubling time (PSADT), are helpful in early detection of occult disease, however they still cannot differentiate between local, regional, or systemic disease to guide further disease management.

The transition to a state of evident metastatic disease (M1) on imaging represents a significant clinical event for both the patients and their treating physicians. Conventional imaging modalities all have low sensitivity and are not able to determine the location of recurrent or metastatic prostate cancer, particularly at low PSA levels.^{4,5,6,7} Thus, imaging agents and modalities that will detect and localize small metastatic lesions, with high sensitivity and specificity, are essential to more accurately diagnose and stage the disease, inform the best treatment strategy and potentially monitor therapeutic response. Early diagnosis of disease recurrence is essential as exemplified by analyses of outcomes post salvage radiotherapy, which is most effective when initiated at PSA levels < 0.5 ng/ml.^{41,42,43}

A number of radiopharmaceutical PET imaging agents have been explored for the detection of prostate cancer, and studied particularly in BCR patients, including 2-deoxy-2-[¹⁸F]fluoro-D-glucose (FDG), ¹¹C-Choline, ¹⁸F-FACBC (¹⁸F-fluciclovine; Axumin), ⁶⁸Ga-HBED-CC (⁶⁸Ga-PSMA-11), and ¹⁸F-DCFPyL.^{7,11,44,45,46,47,48,49} FDG PET, the clinical standard for a number of cancers, has demonstrated mixed results in imaging prostate cancer.^{7,10} Other tumor metabolism-based approaches are the use of radiolabeled choline to take advantage of the increased expression of choline kinase (ChK α) in tumor cells, or increased uptake of amino acids such as methionine or leucine.^{8,9} Although ¹¹C choline was approved by FDA in the BCR setting in 2012, its sensitivity appears limited for extraprostatic lesions and has low detection rates for PSA < 1 ng/mL.^{50,51,52,53} ¹⁸F-fluciclovine (synthetic L-leucine analog trans-1-amino-3-¹⁸F-fluoro-cyclobutane carboxylic acid) PET/CT imaging has been studied in recurrent prostate cancer as well as suspected recurrent prostate cancer,^{46,47,54,55} it was approved by the FDA in 2016 in patients with rising PSA after initial definitive therapy.⁵⁶ However, the detection rate of ¹⁸F-fluciclovine seems to be affected by PSA levels, with higher chance of false positive scans in patients with PSA < 1.8 ng/mL.^{54,56}

The recognition of PSMA as a relatively specific biomarker for prostate cancer has resulted in the development of several diagnostic compounds currently under clinical investigation, with the promise of better sensitivity to detect early, more likely curable stages of metastatic or recurrent prostate cancer. PSMA is highly expressed in castration-resistant, metastatic prostate cancer.²¹ A retrospective evaluation of data from ⁶⁸Ga-PSMA PET/CT imaging in the BCR setting showed 58% detection rate, even in patients with low PSA (0.2 to <0.5 ng/ml).⁴⁸ Studies have also compared ⁶⁸Ga-PSMA PET and ¹⁸F-choline PET imaging, and ⁶⁸Ga-PSMA PET versus ¹⁸F-fluciclovine PET in prostate cancer.^{57,58,59} Comparison of ⁶⁸Ga-PSMA PET to both PET-imaging agents showed significantly higher detection rate and diagnostic accuracy with ⁶⁸Ga-PSMA PET in prostate cancer, including patients with recurrent prostate cancer as well as those with suspected recurrence (BCR).^{49,58}

Nevertheless, fluorine-18 (F-18) PET tracers offer important advantages over PET tracers labeled with other radionuclides, including Ga-68, such as higher production capacity, longer half-life, and improved image resolution. Thus, ¹⁸F-DCFPyL, a PSMA PET-imaging agent, promises to be a useful diagnostic candidate for the detection of metastatic or recurrent prostate cancer, including in the BCR setting where there remains a high unmet medical need.

2. TRIAL OBJECTIVES AND PURPOSE

2.1. Primary Objective

To determine the Correct Localization Rate (CLR) of ¹⁸F-DCFPyL PET/CT imaging in the detection of recurrent prostate cancer at the subject level

2.2. Secondary Objectives

1. To assess the impact of ¹⁸F-DCFPyL PET/CT disease detection on patient's clinical management plans
2. To evaluate the safety and tolerability of ¹⁸F-DCFPyL

2.3. Exploratory Objectives

1. To determine detection rates of disease sites with ¹⁸F-DCFPyL PET/CT by region (prostatic, pelvic, extra-pelvic) and baseline PSA
2. To determine the Positive Predictive Value (PPV) of ¹⁸F-DCFPyL PET/CT imaging in the detection of recurrent disease in the prostatic, pelvic, and extra-pelvic regions

3. TRIAL ENDPOINTS

3.1. Primary Endpoint

The CLR at the subject level, defined as the percentage of subjects for whom there is a one-to-one correspondence between localization of at least one lesion identified on ¹⁸F-DCFPyL PET/CT imaging and the composite truth standard (See [Section 8.1](#))

3.2. Secondary Endpoints

3.2.1. Secondary Efficacy Endpoints

- The percentage of subjects with a change in intended prostate cancer treatment plans due to ¹⁸F-DCFPyL PET/CT as measured by comparison of intended management questionnaires completed Pre- and Post- ¹⁸F-DCFPyL PET/CT imaging results

3.2.2. Safety Endpoints

- Incidence of treatment-emergent adverse events from time of ¹⁸F-DCFPyL dosing up to 7 (±3) days following ¹⁸F-DCFPyL dosing
- Change from Baseline to post ¹⁸F-DCFPyL injection vital signs

- Concomitant medications and medical procedures

3.3. Exploratory Endpoints

- The detection rates of ¹⁸F-DCFPyL PET/CT among lesion locations i.e., prostatic, pelvic, extra-pelvic
- The PPV of ¹⁸F-DCFPyL PET/CT for prostatic, pelvic, extra-pelvic regions from the composite truth standard in subjects with positive lesion(s) on ¹⁸F-DCFPyL PET/CT imaging
- The percentage of subjects with positive ¹⁸F-DCFPyL PET/CT scans who have negative findings for prostate cancer based on the composite truth standard
- The detection rates of ¹⁸F-DCFPyL PET/CT imaging as a function of baseline PSA groups

4. INVESTIGATIONAL PLAN

4.1. Overall Study Design

This is a phase 3, multi-center, open-label, single-arm, non-randomized study to evaluate the diagnostic performance and safety of ¹⁸F-DCFPyL (PyL) PET/CT in subjects with suspected recurrence of prostate cancer and negative or equivocal findings per institutional standard of care conventional imaging. This study is planned to be conducted in approximately 15 sites in the United States and Canada, and to be conducted in conformance with Good Clinical Practices (GCP).

Eligible subjects (see [Section 5](#) for Eligibility Criteria) will be enrolled in a non-randomized, sequential manner, with competitive enrollment between study sites. Enrolled subjects will receive a single dose of 9 mCi (333 MBq) ¹⁸F-DCFPyL Injection followed by a single PET/CT scan acquired at 1-2 hours post-dosing.

Only subjects with positive PyL PET/CT scans (detection of disease at any site) will be followed at the Efficacy visit(s) (See [Table 3](#) Schedule of Assessments). Subjects will undergo Efficacy follow-up based on their PyL PET/CT finding(s) per local interpretation and clinical presentation for evaluation of the composite truth standard as defined in [Section 8.1](#).

If biopsy or surgery of a lesion identified on PyL PET/CT is feasible, attempts will be made to obtain tissue corresponding to the PyL-suspected lesion(s) within 60 days following PyL PET/CT imaging. If local histopathology results are obtained, they will be recorded in the eCRF and if the results are evaluable for prostate cancer, the subject will complete the study.

If histopathology (from biopsy or surgery) is not evaluable, or biopsy or surgery of the PyL-suspected lesion was not performed, an attempt will be made to anatomically correlate the PyL-suspected lesion(s) with conventional imaging modality per the Investigator's discretion within 60 days following PyL PET/CT imaging. The conventional imaging scan will be sent to the central imaging core lab for review. If the scan is deemed evaluable by the central imaging core lab, the subject will complete the study.

If evaluable histopathology is not available and conventional imaging of the PyL-suspected lesion(s) is not informative, those subjects who are planned to receive locoregional RT without concomitant androgen deprivation therapy (ADT) within 60 days following PyL PET/CT imaging will continue on-study and be followed for PSA changes following RT alone. PSA (total) will be collected every 3 months post-RT alone (until Response is achieved as defined in [Section 8.1](#), for a maximum of up to 9 months total duration) and sent to the central lab for analysis. All other subjects not initiated on locoregional RT alone within 60 days post PyL PET/CT imaging will be discontinued from the study.

Subjects who are initiated on any systemic therapy for prostate cancer (PC) will be discontinued from the study.

[figure not shown]
Once the study reaches the required number of subjects evaluable for calculation of the primary endpoint as described in [Section 10.4.2](#), subject enrollment and follow-up assessments will conclude, and the study database will be locked for analysis. Adverse events (AEs) will be assessed following ¹⁸F-DCFPyL dosing (Day 1), and again via a safety phone call 7 (±3) days post-¹⁸F-DCFPyL dosing to capture any late-occurring AEs.

Medical Management Questionnaires (MMQs) will be completed by the treating investigator at two time-points during the study to capture intended changes in the clinical management for all subjects who underwent ¹⁸F-DCFPyL PET/CT imaging:

- **Prior to ¹⁸F-DCFPyL dosing**, the treating investigator will complete the Pre-PyL MMQ based on baseline clinical information and results from conventional imaging.
- **Post-¹⁸F-DCFPyL imaging**, the treating investigator will complete the Post-PyL MMQ based on the additional result from local interpretation of the ¹⁸F-DCFPyL PET/CT scan, to assess whether an intended change to the initial medical management plan is warranted due to the PyL finding.

See [Figure 1](#) and [Table 3](#) for the study schema and schedule of study assessments. Details on study procedures for each visit are described in [Section 4.3](#).

Figure 1: Study Schema

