4.2. Number of Subjects

Approximately 200 subjects are planned to be enrolled in this study to meet the number of subjects required for assessment of the primary endpoint. The Sponsor will periodically monitor the rate of positive ¹⁸F-DCFPyL PET/CT scans and the number of evaluable subjects that contribute to the efficacy assessment. If the observed rate of positive ¹⁸F-DCFPyL PET/CT scans is lower than expected, the sample size may need to be increased. When the required number of subjects are evaluable for calculation of the primary endpoint, subject enrollment and follow-up assessments will conclude.

See [Section 5](#) for eligibility criteria and [Section 10.1](#) for complete sample size assumptions.

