4.3.4. Post-PyL Intended Management Plan (Day 2-60)

For all subjects who complete the PyL PET/CT scan, the Post-PyL MMQ will be completed by the treating investigator based on the additional result from the local PyL PET/CT scan to document whether a change to the initial intended management plan may be warranted due to the PyL finding. The Post-PyL MMQ should be completed within 60 days following ¹⁸F-DCFPyL PET/CT imaging.

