4.4. Study Duration

Subjects will be deemed enrolled once they sign informed consent and meet all inclusion and no exclusion criteria and complete all screening assessments. The study duration of subject participation from Screening through ¹⁸F-DCFPyL PET/CT imaging and Efficacy visit(s), if applicable, will be a maximum duration of approximately 12 months. At a minimum, all subjects who receive a dose of ¹⁸F-DCFPyL will be followed from time of informed consent until the safety phone call on Day 8 (± 3).

Only subjects with positive PyL PET/CT scans (detection of disease at any site) will be followed at the Efficacy visit(s). Subjects will undergo Efficacy assessments based on the site's local PyL PET/CT interpretation and clinical presentation.

- Subjects with any positive PyL PET/CT finding(s) per local interpretation will be evaluated as described in [Section 4.3.5](#).
- Subjects without any positive PyL PET/CT finding per local interpretation will complete the study through the safety phone call; no further visits will be required.

The Sponsor may conclude the study before subjects complete their efficacy follow-up assessments (see [Section 10.4.2](#))

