10.4.2. Efficacy Analyses

Efficacy endpoints will be assessed using the FAS. Continuous monitoring will be performed with respect to the number of subjects evaluable for the primary endpoint. When the required number of subjects with positive ¹⁸F-DCFPyL PET/CT scans and information for the composite truth standard are available for calculation of the CLR, subject enrollment and follow-up assessments will conclude, and the study database will be locked for analysis. Any subjects who are undergoing efficacy evaluations who have not contributed endpoint data at the time of database lock will be censored and will be treated as unevaluable for efficacy.

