4. STUDY DESIGN

This is a phase 3, multi-center, open-label, single-arm, non-randomized study to evaluate the diagnostic performance and safety of ¹⁸F-DCFPyL (PyL) PET/CT in subjects with suspected recurrence of prostate cancer and negative or equivocal findings per institutional standard of care conventional imaging. This study is planned to be conducted in approximately 15 sites in the United States and Canada, and to be conducted in conformance with Good Clinical Practices (GCP).

Eligible subjects will be enrolled in a non-randomized, sequential manner, with competitive enrollment between study sites. Enrolled subjects will receive a single dose of 9 mCi (333 MBq) ¹⁸F-DCFPyL Injection followed by a single PET/CT scan acquired at 1-2 hours post-dosing.

Only subjects with positive ¹⁸F-DCFPyL PET/CT scans per local interpretation (detection of disease at any location) will be followed for Efficacy follow-up visit(s) (See Table 1 Schedule of Assessments). ¹⁸F-DCFPyL PET/CT scans will be evaluated by three independent central readers blinded to all clinical and other imaging information. ¹⁸F-DCFPyL PET/CT imaging results reported by the central readers will be compared to the composite truth standard of histopathology where available, imaging follow-up, or treatment response as defined in Section 5.1.1.

Once the study reaches the required number of subjects evaluable for calculation of the primary endpoint as described in Section 7.1, subject enrollment and follow-up assessments will conclude, and the study database will be locked for analysis. Adverse events (AEs) will be assessed following ¹⁸F-DCFPyL dosing (Day 1), and again via a safety phone call 7 (±3) days post-¹⁸F-DCFPyL dosing to capture any late-occurring AEs.

Medical Management Questionnaires (MMQs) will be completed by the treating investigator at two time-points during the study to capture planned changes in the clinical management for all subjects who underwent ¹⁸F-DCFPyL PET/CT imaging:

- **Prior to** ¹⁸**F-DCFPyL dosing,** the treating investigator will complete the Pre-PyL MMQ based on baseline clinical information and results from conventional imaging.
- **Post-**¹⁸**F-DCFPyL imaging**, the treating investigator will complete the Post-PyL MMQ based on the additional result from local interpretation of the ¹⁸F-DCFPyL PET/CT scan, to assess whether a planned change to the initial medical management plan is warranted due to the PyL finding.

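### When the evaluable count is reached, follow-up stops along with enrolment, so men already dosed may never supply a truth result or Post-PyL questionnaire that was still obtainable

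*Protocol*

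**What the plan says.** Three protocol sections and the SAP tie the end of follow-up to the evaluable count.

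- Protocol 4.2: "When the required number of subjects are evaluable for calculation of the primary endpoint, subject enrollment and follow-up assessments will conclude". Section 4.1 adds the database lock: "subject enrollment and follow-up assessments will conclude, and the study database will be locked for analysis".
- Protocol 10.4.2 triggers when enough positive scans with "information for the composite truth standard are available for calculation of the CLR, subject enrollment and follow-up assessments will conclude". It continues: "Any subjects who are undergoing efficacy evaluations who have not contributed endpoint data at the time of database lock will be censored", and such men are treated as unevaluable for efficacy.
- Protocol 4.4: "The Sponsor may conclude the study before subjects complete their efficacy follow-up assessments". The minimum it guarantees every dosed man is follow-up to the Day 8 safety call.
- SAP section 4 repeats the rule: "Once the study reaches the required number of subjects evaluable for calculation of the primary endpoint as described in Section 7.1".

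On the management questionnaire (MMQ), protocol 4.3.4 says: "For all subjects who complete the PyL PET/CT scan, the Post-PyL MMQ will be completed by the treating investigator". On timing: "The Post-PyL MMQ should be completed within 60 days following" the scan. Note 9 to Table 3 repeats that it is due for all scanned men. The secondary endpoint built on it is analysed on the whole FAS, whatever the scan result (protocol 10.4.2.2, SAP 8.5.3).

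The truth standard (protocol 8.1) allows 60 days for histology or conventional imaging. For men treated with RT alone it allows PSA follow-up every 3 months for up to 9 months.

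**The concern.** At the trigger, the most recently dosed men are still inside their 60-day window, and PSA-route men may be months from a settled result. Nothing in either document lets them finish. Three things are at stake.

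1. The primary CLR rests on fewer men than were dosed and could have been verified.
2. The last men scanned may have no Post-PyL MMQ, although the form is required of all of them and feeds a full-FAS endpoint.
3. On the PSA route, whether a man is counted by lock depends on his outcome. A confirmed responder can be a true positive from about month 3. A non-responder is settled as a false positive only at month 9. A cut-off between those dates keeps responders and drops non-responders.

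**Working it through.** **The plan's own figures.** With CLR 0.30 and target lower limit 0.20 (protocol 10.1, SAP 7.1), n = 1.96² × 0.30 × 0.70 / 0.10² = 80.7, so 81. Then 80.7 / 0.60 = 134.5 (stated as 134), and 134 / 0.70 = 191.4, so 192. The sample size reproduces.

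**Men in the pipeline at the trigger.** The documents give no accrual rate. I assume 192 scans over 6, 12 or 18 months, and results spread evenly over the 60 days (2 months), so that half are pending. The plan's 60% positive and 70% evaluable rates give a factor of 0.42.

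| Enrolment | Scans/month | In 60-day window | Evaluable (× 0.42) | Pending (half) |
|---|---|---|---|---|
| 18 months | 10.7 | 21 | 9.0 | 4.5 |
| 12 months | 16 | 32 | 13.4 | 6.7 |
| 6 months | 32 | 64 | 26.9 | 13.4 |

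Simulated accrual with lock at the 81st evaluable man agrees: about 22 to 64 men in the window and about 5 to 14 pending histology or imaging results.

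**Precision.** Completing those results gives about 85 to 94 evaluable men. Half-width = 1.96 × √(0.21 / n): 9.98 points at n = 81, 9.74 at 85, 9.26 at 94.

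**Chance of success, one reader.** Success needs a Wald lower limit above 0.20. At n = 81 this takes 25 true positives (24 gives 0.197, 25 gives 0.208). Exact binomial probabilities:

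| n | TP needed | Success if CLR 30% | Success if CLR 20% |
|---|---|---|---|
| 81 | 25 | 47.4% | 1.35% |
| 84 | 26 | 46.5% | 1.15% |
| 85 | 26 | 49.4% | 1.35% |
| 88 | 26 | 57.7% | 2.11% |
| 89 | 27 | 51.2% | 1.34% |
| 93 | 28 | 53.0% | 1.33% |
| 94 | 28 | 55.7% | 1.54% |

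The probability moves in a sawtooth. At about the same false-success rate as n = 81, it rises to 51 to 53% (n = 89 or 93).

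**PSA route.** Neither the share of men on this route nor their response times are stated. I assumed a true CLR of 30%, 10 to 30% of evaluable men on the route, RT starting evenly over 60 days, responders confirmed about two weeks after month 3, 6 or 9 (40%, 40%, 20%), and non-responders settled at month 9. At 10 to 30 scans a month, mean CLR at lock was 30.3% to 32.6%; full follow-up of the same men gave about 30%. Across the simulations run, the excess was about 0.2 to 2.6 points. With no PSA-route men it was nil. Waiting 60 days before lock barely changes this excess: with 6-month enrolment and a 30% share, the mean was 32.6% both before and after the wait.

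**MMQ passages side by side.** Section 4.3.4 stands apart from Efficacy Follow-up (4.3.5) and requires the form from every scanned man. Table 3, however, lists the Post-PyL form in the Efficacy follow-up columns, the activity that ends at the trigger. No passage says whether outstanding forms are collected before lock.

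**The case against.** Stopping on an evaluable count is a disclosed design choice, and several stronger readings go beyond the text.

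- *The database locks at once and results are thrown away.* A reader might infer this, but no interval between trigger and lock is stated. Results in hand at lock are kept; pending ones are simply never obtained.
- *The plan orders Post-PyL forms to be dropped.* It does not. The censoring sentence concerns men undergoing efficacy evaluations, and the form remains required. The form also needs only the local read, so 22 to 64 is a ceiling on missing forms, not an expected loss. What stands is an unresolved conflict.
- *CLR depends on the lock date in general.* Not shown. For histology and imaging, nothing in the documents links speed of result to outcome. The bias needs PSA-route men, and its size rests on assumed shares and response times.
- *The rule costs substantial power.* Much of the apparent gain is Wald discreteness. The 47% at n = 81 is a sample-size matter, not an effect of the lock rule.

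The SAP also plans multiple imputation and a tipping-point analysis for positive scans with missing or unevaluable truth (8.5.2.2). Every delta is negative, so the analysis probes the direction of concern. That is a real mitigation, but these are sensitivity analyses of the primary endpoint only. They do not cover the MMQ, and imputing by PSA group or truth method does not model time to result.

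**Conclusion.** The point holds in limited form. Follow-up ends with enrolment in all four places, and men without endpoint data at lock become unevaluable. About 5 to 14 histology or imaging results obtainable within 60 days go uncollected, assuming 192 scans over 6 to 18 months, 60% positive, 70% evaluable and results spread evenly. Collecting them would narrow the half-width by about 0.3 to 0.7 points; the power gain is small and not monotone in n. The lock rule and the MMQ requirement must be reconciled.

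The PSA-route cut-off biases CLR upward by about 0.2 to 2.6 points if 10 to 30% of evaluable men use that route, and not at all if none do. Table 4 of the SAP adds uncertainty: its false-positive row does not say how to class a man with only early PSA values at lock. Counting him as a false positive would push CLR the other way. The 81, 134 and 192 are not in question.

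**What to change.** In protocol 4.1, 4.2, 4.4 and 10.4.2 and SAP section 4:

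1. Let the count close enrolment only. Name the count (10.4.2 gives no number, and SAP 7.1 attaches the word evaluable to 134 scans rather than to the 81 positives) and the read that defines it.
2. Lock after every dosed man has completed the 60-day efficacy window and the Post-PyL MMQ. Analyse all of them, even if the count exceeds the target.
3. For PSA-route men still open at that date, keep observed results in the primary analysis, and do not class a man as a false positive before his month-9 value.
4. Because the 60-day wait does not remove the PSA-route bias, prespecify a sensitivity analysis of CLR. Either limit PSA-route men, responders and non-responders alike, to those whose RT began at least 9 months before lock, or exclude the PSA route. This should not be the primary analysis: it would drop confirmed responders already observed and could take the evaluable count below target.

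Cost: wording changes and up to about 60 days' delay to lock. No added patients or procedures.
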